3.2 STUDY DESIGN: INDONESIA (BCOV21 AND BCOV22)

The BCOV21 Trial was a single-blind five-arm randomised controlled non-inferiority trial sponsored by the Indonesian Government looking at the immunogenicity, safety, and reactogenicity over 3 months of fractional vs. standard doses of COVID-19 vaccines (Pfizer-BioNTech [Comirnaty®] and AstraZeneca [Vaxzevria®]) in healthy adults aged 18 years or older in Indonesia who have received two primary doses of either CoronaVac® 3-5 months prior to enrolment, CoronaVac® 6-9 months prior to enrolment, or Vaxzevria® 6-9 months prior to enrolment.

The trial was conducted at Bandung and Jakarta, Indonesia. 1000 participants who had been primed with *CoronaVac*® (3-5 months or 6-9 months prior to enrolment) were randomised 1:1:1:1:1 to fractional or standard doses of *Comirnaty*® or *Vaxzevria*®, or a standard dose of *CoronaVac*®, with stratification by the primary vaccine received (*CoronaVac*® 3-5 months prior or *CoronaVac*® 6-9 months prior) and age (<60 and ≥60 years) to ensure balance between the arms with respect to these key factors. Additionally, 400 participants who had been primed with *Vaxzevria*® 6-9 months prior to enrolment were randomised 1:1:1:1 to fractional or standard doses of *Comirnaty*® or *Vaxzevria*®, with stratification by age (<60 and ≥60 years) to ensure balance between the arms with respect to age. Recruitment within each stratum was stopped once quotas were reached to ensure that the number of participants in each of the primary series strata were equal and that 20% of participants were ≥60 years of age (recruitment into the older age stratum fell slightly short of the quotas).

Participants were followed for 28 days. Recruitment and follow up for BCOV21 had finished at the time of writing the SAP. Immunogenicity outcomes (humoral immunity only) were measured at baseline and 28 days. Safety and reactogenicity outcomes were collected from baseline to 7 days (solicited AE), 28 days (unsolicited AE).

Rescue vaccination was offered to participants who received *CoronaVac*® based on Day-28 outcomes, which was taken up by most participants in the *CoronaVac*® arm; the rescue vaccination was provided under the public health system.

The BCOV22 Observational Study (sponsored by MCRI) has invited all participants of BCOV21 for extended follow-up to 12 months, with immunogenicity outcomes measured at Month-6 and Month-12 (timepoints from the start of BCOV21). Day-28 BCOV21 samples not previously analysed for some immunogenicity outcomes will be tested as part of BCOV22.

3.3 STUDY DESIGN: MONGOLIA TRIAL

The Mongolia Trial is a single-blind two-arm randomised controlled non-inferiority trial (1:1) looking at the immunogenicity, safety, and reactogenicity over 12 months of fractional vs. standard doses of the COVID-19 vaccine Pfizer-BioNTech [Comirnaty] in healthy adults aged 18 years or older in Mongolia who have received two primary doses of either Sinopharm [Covilo®], AstraZeneca [Vaxzevria®], Gamaleya [Sputnik®] vaccines 6 months prior to enrolment.

The trial will be conducted at multiple sites (vaccination clinics) in Ulaanbaatar. Participants will be randomised 1:1 to fractional or standard doses of Comirnaty®, with 400 participants per arm, and stratification by the primary vaccine received (Covilo®, Vaxzevria®, or Sputnik®) (target recruitment quotas 200:100:100) and age (<50 and ≥50 years) (target recruitment quotas 200:200) to ensure balance between the arms with respect to these key factors. Additionally, 40% of participants from each study group will be included in a sub-study of cell-mediated immunity (CMI).

Participants will be followed for 12 months. Immunogenicity outcomes (humoral and cellular immunity) will be measured at baseline, 28 days, 6 months, and 12 months. Safety and reactogenicity outcomes will be collected from baseline to 7 days (solicited AE), 28 days (unsolicited AE), 3 months (medically attended AE), and 12 months (SAE).

The protocol specifies that if fractional dose responses are considered inadequate (undefined) an appropriate rescue strategy will be developed, probably involving a single dose (dosage not specified) of the vaccine in question at 3 months.

3.4 STUDY GROUPS AND RANDOMISATION

Table 1 provides a brief description of the trial vaccines. Further information on the trial vaccines, including active substances, mode of action, dosage, and administration are provided in the Protocols. Dose modifications are not permitted and must be given as per randomisation.

Table 1. Summary of trial vaccines

Country	Study Group	Generic vaccine name	Route	Dose
Indonesia Trial	Comirnaty® standard full dose	Pfizer-BioNTech (BNT162b2)	IM	30µg
	Comirnaty® fractional dose	Pfizer-BioNTech	IM	15μg

		(BNT162b2)		
	Spikevax® standard full dose	Moderna (mRNA-1273)	IM	50μg
	Spikevax® fractional dose	Moderna (mRNA-1273)	IM	20μg
	Vaxzevria® standard full dose	AstraZeneca (ChAdOx1-S)	IM	5 x 10 ¹⁰ vp in 0.5ml
	Vaxzevria® fractional dose	AstraZeneca (ChAdOx1-S)	IM	2.5 x 10 ¹⁰ vp in 0.25ml
Indonesia	Comirnaty® standard full dose	Pfizer-BioNTech (BNT162b2)	IM	30µg
	Comirnaty® fractional dose	Pfizer-BioNTech (BNT162b2)	IM	15µg
BCOV21/22	Vaxzevria® standard full dose	AstraZeneca (ChAdOx1-S)	IM	5 x 10 ¹⁰ vp in 0.5ml
	Vaxzevria® fractional dose	AstraZeneca (ChAdOx1-S)	IM	2.5 x 10 ¹⁰ vp in 0.25ml
	CoronaVac® standard dose	Sinovac	IM	3μg or 600 SU in 0.5ml
Managha Talah	Comirnaty® standard full dose	Pfizer-BioNTech (BNT162b2)	IM	30µg
Mongolia Trial	Comirnaty® fractional dose	Pfizer-BioNTech (BNT162b2)	IM	15µg

IM: Intramuscular. Colours are used to highlight common study groups across countries.

	Spikevax® standard full dose	200	Comparison (to Spikevax®	Vaxzevria*	≥50 years	50
	Spikevax standard run dose	200	fractional dose)	CoronaVac®	<50 years	50
				CoronaVac®	≥50 years	50
	Spikevax® fractional dose	200		Vaxzevria*	<50 years	50
			Intervention - Spikevax®	Vaxzevria®	≥50 years	50
			incervention - Spikevax	CoronaVac®	<50 years	50
				CoronaVac®	≥50 years	50
				Vaxzevria*	<60 years	50
				Vaxzevria*	≥60 years	50
	Comirnaty® standard full dose	300^	Comparison (to Comimaty®	CoronaVac® 3-5m	<60 years	50
	Standard rail dose	300	fractional dose)	CoronaVac® 3-5m	≥60 years	50
				CoronaVac® 6-9m	<60 years	50
				CoronaVac® 6-9m	≥60 years	50
				Vaxzevria*	<60 years	50
				Vaxzevria*	≥60 years	50
Indonesia BCOV21/22	Comirnaty® fractional dose	300^	Intervention - Comimaty®	CoronaVac® 3-5m	<60 years	50
				CoronaVac® 3-5m	≥60 years	50
				CoronaVac® 6-9m	<60 years	50
				CoronaVac® 6-9m	≥60 years	50
				Vaxzevria*	<60 years	50
			Comparison (to Vaxzevria®	Vaxzevria*	≥60 years	50
	Vaxzevria® standard full dose	300^	fractional dose)	CoronaVac® 3-5m	<60 years	50
			,	CoronaVac® 3-5m	≥60 years	50
				CoronaVac® 6-9m	<60 years	50

				CoronaVac® 6-9m	≥60 years	50
				Vaxzevria*	<60 years	50
				Vaxzevria*	≥60 years	50
				CoronaVac® 3-5m	<60 years	50
	Vaxzevria® fractional dose	300^	Intervention - Vaxzevria®	CoronaVac® 3-5m	≥60 years	50
				CoronaVac® 6-9m	<60 years	50
				CoronaVac® 6-9m	≥60 years	50
				CoronaVac® 3-5m	<60 years	50
	CoronaVac® standard dose	2004	NA	CoronaVac® 3-5m	≥60 years	50
	Corona vac ^a standara dose	200^	NA NA	CoronaVac® 6-9m	<60 years	50
				CoronaVac® 6-9m	≥60 years	50
	Comirnaty® standard full dose	400		Covilo®	<50 years	100
				Covilo®	≥50 years	100
			Comparison (to Comimaty® fractional dose)	Vaxzevria®	<50 years	50
				Vaxzevria®	≥50 years	50
				Sputnik®	<50 years	50
Mongolia Trial				Sputnik®	≥50 years	50
(1:1)				Covilo®	<50 years	100
				Covilo®	≥50 years	100
	Comimate® fractional dosa	400	Interpretion Comimates	Vaxzevria®	<50 years	50
	Comirnaty® fractional dose	400	Intervention - Comimaty®	Vaxzevria®	≥50 years	50
				Sputnik*	<50 years	50
				Sputnik®	≥50 years	50

*In addition to the primary series and age strata, participants will be stratified for inclusion into a CMI sub-study: 80 participants from each arm in Indonesia (total 480); 40% of participants from each stratum in Mongolia (total 160). *These groups will be supplemented with concatenated data from BCOV21/22 (up to 300 participants per study group) in a combined analysis. 3-5m and 6-9m refers to the months prior to enrolment that the primary series was received. ^Numbers are for recruitment into BCOV21; numbers in BCOV22 will depend on recruitment rates into BCOV22. Further, BCOV21 recruitment has finished and fell short of recruitment targets in the CoronaVac primed ≥60 years group by 40 participants across all arms.

3.5 BLINDING

Study staff involved in administering the vaccine will be unblinded. The participants and study staff involved in assessing reactogenicity will be blinded to their group allocation until the Day-28 visit. Study staff involved in assessing immunogenicity outcomes will remain blinded during the analysis of specimens. In the unlikely event that it becomes necessary to unblind prior to the Day-28 visit that decision will be taken by the PI, and the participant and physicians who may be caring for the participant will be made aware of the allocation. Statisticians and analysts will remain blinded during the development of the SAP (approved by the Trial Steering Committee). Further, statisticians and analysts will develop and finalise all codes using a dummy variable for treatment allocation. If SAP revisions related to comparative analyses are required after codes have been run using the real allocations, the staff involved in deciding, writing, and approving these revisions will not have access to the data with the real allocations.

3.6 STUDY POPULATION: ELIGIBILITY AND SCREENING

The study populations and Pre-Screening methods for each country are detailed in the sections below.

In all countries, participants are consented at the Day-0 visit (after Pre-Screening), and a post-consent assessment is conducted to determine final eligibility. Those who provide consent but are determined to be ineligible are termed screen failures. The number of screen failures will be reported with reasons.

3.6.1 Indonesia Trial

Trial participants will be healthy adults aged 18 years or older in Indonesia who have received two primary doses of either Sinovac [CoronaVac*] or AstraZeneca [Vaxzevria*] 6 months prior to enrolment. Participants will be recruited from three clinics (Garuda, Ciumbuleuit, and Dago) in Bandung, West Java, Indonesia. Inclusion and exclusion criteria are listed in the Protocol.

At each recruiting clinic, records of COVID-19 immunization will be reviewed to identify potential participants (adults who have received two priming doses of *Vaxzevria*® or *CoronaVac*® over 6 months ago and have not yet received a third dose) (Pre-Screening). Potential participants will be contacted by the clinic personnel to give initial information about the study and invite the potential participant to attend an in-person screening visit. A record of all potential participants from Pre-Screening who attend the in-person screening visit will be recorded in a recruitment log. If the potential participant decides not to participate no identifying information will be retained.

3.6.2 Indonesia BCOV22 Observational Study

Trial participants will be healthy adults aged 18 years or older in Indonesia who have received two primary doses of either Sinovac [CoronaVac®] or AstraZeneca [Vaxzevria®], and who were enrolled into BCOV21. BCOV21 recruited participants from Bandung and Jakarta, Indonesia. All BCOV21 participants will be approached for recruitment into BCOV22. Inclusion and exclusion criteria are listed in the Protocol.

3.6.3 Mongolia Trial

Trial participants will be healthy adults aged 18 years or older in Mongolia who have received two primary doses of either Sinopharm [Covilo*], AstraZeneca [Vaxzevria*], or Gamaleya [Sputnik*] 6 months prior to enrolment. Participants will be recruited at multiple sites (vaccination clinics) in Ulaanbaatar. Inclusion and exclusion criteria are listed in the Protocol.

81803 (V9), 81800 (V4), BCOV22 (V3)

Statistical Analysis Plan

Page 15 of 52

The study will be offered to people attending participating clinics for their third dose (Pre-Screening). Those interested will be provided with the participant information sheet and consent form and a member of the research team will be available to answer their questions. If recruitment is slow, the study may be promoted by the Ministry of Health through their daily media briefings. A record of all potential participants from Pre-Screening will be recorded on a recruitment log. If the potential participant decides not to participate no identifying information will be retained.

3.7 SAMPLE SIZE

Details of sample size calculations are provided in the protocols.

3.8 STUDY PROCEDURE

Figure 1 provides a summary of the study procedures. A participant will be considered lost to follow-up if they fail to return for two consecutive visits and cannot be contacted by the trial staff.

	Day 0	Day 1	Day 7	Day 28	Month 3	Month 6	Month 12	
General	Informed consent Big-billy confirmation Val signs (before and after vaccination) Issue dary card, ruler, and thermonster Demographics Height & weight Dates & type of primary COVID-19 vaccine Comorbidities Concomitant medication	(Phone call visit)	Collect diary card		(Phone call visit)		Gift Test results shared and discussed on request	
Intervention	Randomisation Vaccination			Unblinding				
Immunogenicity	Blood sampling (pre- vaccination)			Blood sampling		Blood sampling	Blood sampling	
Safety	Immediate AE within 15 minutes of vaccination	COVID-19 infection Review & document: Solicited AE* Unsolicited AE* Medically attended AE*	COVID-19 infection Review& document: Solicited AE* Unsolicited AE* Medically attended AE*	Unsolicited AE Medically attended AE COVID-19 infection	New information regarding unsolicited AE to day 28, such as resolution Medically attended AE COVID-19 infection	Receipt of 4 th COVID-19 vaccination	Receipt of 4 th COVID-19 vaccination	
Unscheduled		 Documentation of SAE and COVID-19 infection throughout study period (participants instructed to contact study staff) Withdrawal dates and reason 						

^{*} Self-documented daily by participant between days 1 and 7, inclusive.

Figure 1. Timeline of trial procedures. BCOV22 begins at the Month 6 visit; data will be concatenated with BCOV21, providing data for all visits prior to Month 6 (Day 0 – Day 28).

4 OUTCOME VARIABLES AND OTHER PARAMETERS

4.1 IMMUNOGENICITY OUTCOMES

Table 3 describes the immunogenicity outcome variables.

Table 3. Description of outcome variables

	Outcome	Subset	Units	Timepoints^
Humoral	Seroresponse (see 5.1.1 for	All	Binary (yes/no)	Day 28
immunity	definition)		billary (yes/110)	Day 20

(antibodies)	Binding antibody (IgG) ACE2 binding* inhibition by	ACE2 binding inhibition was measured for only a subset of participants in BCOV21 (Day-28) – BCOV22 will complete measurements for all participants using samples collected in BCOV21.	BAU/ml#	Day 28 Month 6 Month 12
	neutralising antibody (wild type) ACE2 binding* inhibition by neutralising antibody (Omicron)		% Binding inhibition	Day 28 Month 6 Month 12
	Neutralising antibody (wild type)	MCRI-Mongolia Trial: 20% in Mongolia		
	Neutralising antibody (Delta)	Indonesia Trial: 40 participants in the Spikevax® arms (10 per primary vaccine strata for each dose allocation group) BCOV22: 140 participants (10 per primary vaccine strata for each dose allocation group and trial vaccine)	NT50	Day 28 Month 6 Month 12
	Neutralising antibody (Omicron)			
	ΙΕΝγ		IU/ml	Day 28 Month 12
Cellular immunity	IFNγ-producing cells	Indonesia Trial: 80 participants per arm (480 total)	cells/million PBMCs	Day 28 Month 12
(CMI sub-study)	Cytokine-expressing T cells (multiple outcomes for several cytokines^)	Mongolia Trial: 40% per strata (160 total) BCOV22: no CMI analysis (0 total)	Frequency (%) of cell subset	Day 28 Month 12

	Cytokine concentration (multiple outcomes for several cytokines [^])		pg/ml	Day 28 Month 12
--	--	--	-------	--------------------

^{*}Between the SARS-CoV-2 receptor binding domain and the host-cell ACE2 (angiotensin converting enzyme-2) receptor. *Binding antibody will be measured as relative units/ml (RU/ml) as per the manufacturer's instructions, and converted to binding antibody units (BAU/ml) using the WHO reference serum from NIBSC, UK. Specific cytokines are yet to be specified. *Baseline measurements are also taken at Day 0.

4.2 REACTOGENICITY AND SAFETY OUTCOMES

Table 4 summarises the reactogenicity and safety outcomes and relevant parameters. Further details on all collected parameters are stored in RedCAP Codebooks, as detailed in the Data Management Plan. Definitions of the terms adverse event, adverse reaction, and serious adverse event are given in the Protocols, and are aligned with definitions used in trials involving investigational medicinal products.

Table 4. Reactogenicity and safety outcomes

Outcome	Parameter	Categories	Timepoints	
	Pain			
	Tenderness			
	Redness	Grade 0, 1, 2, 3, or		
	Swelling	4*		
Reactogenicity (local)	Hardness] 4		
	Axillary			
	lymphadenopathy			
	Warmth	Binary	Day 1, 2, 3, 4, 5, 6, &	
	Itch	(presence/absence)	7	
	Fever			
	Nausea			
	Vomiting	Grade 0, 1, 2, 3, or		
Reactogenicity (general/systemic)	Diarrhoea	4*		
	Headache	4		
	Fatigue/Malaise			
	Myalgia			

	Arthralgia			
	Experienced an adverse event	Binary (yes/no)		
	System Organ Class [^]	As per MedDRA		
	Severity	Severity Grade 1 (mild), 2 (moderate), 3 (severe), 4 (life- threatening), 5 (fatal)#	Adverse Events to 28 Days: Day-0, -1, -7, and -28 visits, and	
Adverse Events to 28 Days Adverse Reaction to 28 Days ⁸ Serious Adverse Events to 12 months	Outcome	1-Resolved 2-Resolved with sequelae 3-Ongoing 4-Fatal 5-Unknown	Month-3 visit (for new information, e.g., resolution) Serious Adverse Events to 12 months:	
	Serious	Binary (yes/no)	Unscheduled (participants instructed to contact	
	Onset (days from trial vaccination)	Continuous	study staff)	
	Event duration (days)	Continuous	study starry	
	Relatedness	1-Unrelated 2-Possible 3-Probable 4-Definite		

^{*5-}point severity scale: 0-None; 1-Mild; 2-Moderate; 3-Severe; 4-Life-threatening. Refer to Protocol for more detailed definitions. Grading for hardness and swelling in Mongolia will not consider interference with daily activities as per the protocol as this information is not being captured. #Grade 3-4 events may be SAEs; all Grade 5 events are automatically considered as SAEs. ^Will require derivation from 'event_term' and 'saefin' fields by study team. ⁸An adverse reaction is an adverse event with causality assessment of either Possible, Probable, or Definite.

4.3 DEMOGRAPHY AND BASELINE

At the Day 0 visit, information is collected on the participant's primary series (including vaccine, dates, and any reactions experienced), demographics (age, sex, ethnicity), comorbidities, and clinical observations prior to trial vaccination. Details of demography and baseline parameters are stored in RedCAP Codebooks, as detailed in the Data Management Plan.

4.4 INTERCURRENT EVENTS

Data will be collected throughout the 12-month follow-up period on receipt of a 4th dose (including date and vaccine) and breakthrough SARS-CoV-2 infections (including date and severity). These will be considered as intercurrent events in the analysis; the strategies that will be used for handling these events are detailed in Estimand-to-Analysis tables in 6.13 Analysis of the primary endpoints and 6.14 Analysis of secondary endpoints. Intercurrent event parameters are detailed in Section 4.4 Intercurrent events.

Intercurrent event	Potential impact if ignored
Breakthrough SARS-CoV-2 infection	Breakthrough infections will have a boosting effect on
	immunological markers, making the trial vaccine appear more
	immunogenetic than it truly is. High incidence of breakthrough
	infections due to reduced immunogenicity in one group could give
	the appearance of greater immunogenicity of the trial vaccination in
	this group relative to other groups in which breakthrough infections
	have been more successfully prevented.
Receipt of 4th dose (self-initiated or	Receipt of a 4 th dose will have a boosting effect on immunological
sponsor-initiated, i.e. rescue)	markers, making the trial vaccine appear more immunogenetic than
	it truly is. Higher uptake of the 4th dose in one group (e.g. due to
	rescue of fractional dose recipients) could give the appearance of
	greater immunogenicity of the trial vaccination in this group relative
	to other groups with lower 4 th dose uptake.

Lost-to-follow-up and other events resulting in missing data will be treated as a missing data problem and handled using multiple imputation.

5 ENDPOINTS

5.1 PRIMARY ENDPOINTS

5.1.1 Seroresponse at Day-28

The primary endpoint is seroresponse at the Day-28 visit, comparing the fractional dose group to the standard dose group for each booster vaccine. Seroresponse at the individual level is defined as a \geq 4-fold rise in binding antibodies at the Day-28 visit compared to baseline (prevaccination), or a \geq 2-fold rise among participants with a baseline (pre-vaccination) titre of \geq 200 BAU/ml (Table 5).

Table 5. Thresholds to define seroresponse in an individual at the Day-28 visit, by baseline binding antibody titre

Baseline binding antibody titre	Threshold for seroresponse at 28 days
Below limit of detection (<100 BAU/ml)	≥ 4 x lower limit of detection (100 BAU/ml) ("4-fold rise"), i.e. ≥ 400
	BAU/ml
<200 BAU/ml	≥ 4 x baseline ("4-fold rise")
≥200 BAU/ml	≥ 2 x baseline ("2-fold rise")

5.1.2 Reactogenicity within 7 days of boosting

Reactogenicity will be measured using a standardised daily questionnaire (diary card) that elicits the presence and severity (mild, moderate, severe, life-threatening [grades 1-4, respectively]), or absence, of local reactions (pain, tenderness, redness, hardness, swelling, necrosis, warmth, or itch at or near the injection site) or systemic reactions (fever, nausea, vomiting, diarrhoea, headache, fatigue/malaise, myalgia, arthralgia, or enlarged lymph nodes) within the last 24 hours on days 1 through 7. Warmth and itch will be recorded as presence/absence only (i.e., not graded). The primary endpoint for reactogenicity will be solicited grade 3 or 4 local or systemic reactions within 7 days of vaccination, inclusive.

Table 6. Primary endpoints

Primary Endpoint	Outcome	Timepoint	Population measure	Comparison	Measure of association
i.	Seroresponse (see Table 5)	Day-28 visit	% (95% CI)	Fractional vs. Standard	Difference in %
ii.	Reactogenicity: solicited grade 3 or 4 local or systemic reactions within 7 days of vaccination, inclusive	7 days post- booster	% (95% CI)	NA (descriptive)	NA (descriptive)

All analyses will be conducted separately for the different booster vaccines, amongst all strata combined, and then stratified by the primary series strata (see

Strategy for multiple imputation

Protocol Numbers:

81803 (V9), 81800 (V4), BCOV22 (V3)

Statistical Analysis Plan

Page 22 of 52

Multiple imputation will be done using a multivariate imputation model (MICE) and 50 imputations. Covariates in the imputation model will be the same as those specified for imputation under the hypothetical strategy (Section 6.15.1 Implementation of the Hypothetical Strategy). For the binary seroresponse outcome, binding antibody levels will be imputed (rather than the relative increase from baseline or binary seroresponse), and then seroresponse will be derived using the imputed value/s.

Subgroup analyses and tests for interaction).

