
Statistical Analysis Plan

Page 38 of 52

irrespective of breakthrough infections or receipt of a 4 th dose (self-initiated).	4 th dose.	Receipt of 4 th dose (self-initiated): Hypothetical ⁸	-no participants received a self- initiated 4 th dose	
--	-----------------------	--	--	--

"This row is generic for all immunological endpoints at the specified timepoint (Table 7). The specified supplementary analyses will be conducted for each endpoint, separately for each trial vaccine. A This row is generic for the Month-6 and Month-12 timepoints. Under the hypothetical strategy, outcome values experienced after the specified intercurrent events will be set to missing and multiple imputation will be used to calculate the estimate including these participants. The parts of the Estimands and intercurrent event strategies that are being modified in the each of supplementary analyses are highlighted by blue text.

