6.15.1 Implementation of the Hypothetical Strategy

Under the hypothetical strategy, outcome values experienced after the specified intercurrent events will be set to missing and multiple imputation will be used to calculate the estimate including these participants. For the binary seroresponse outcome, binding antibody levels at Day 28 will be imputed, and then seroresponse will be derived using the imputed value. Multiple imputation will be done using a univariate regression imputation model (logistic regression for binary outcomes and linear regression for continuous outcomes) and 50 imputations. Covariates in the imputation model will be:

- trial vaccine
- study arm (fractional/standard)
- primary series vaccine
- age group
- duration between 1st and 2nd
- duration between 2nd and 3rd doses
- · study day of blood draw
- baseline levels of the outcome variable (for seroresponse, baseline binding antibody as a continuous variable will be included).
- For Month-6 and Month-12 endpoints, levels of the outcome variable at previous blood draws will also be included if the intercurrent
 event occurred after these visits.

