6.16 SUBGROUP ANALYSES AND TESTS FOR INTERACTION

Analyses will be conducted separately for each study (the Indonesia Trial, BCOV22 [concatenated with BCOV21], and the Mongolia Trial). Analyses will also be conducted on concatenated data of the Indonesia Trial and BCOV21/22.

Analyses for all endpoints will be conducted separately for the different booster vaccines, amongst all strata combined. Subgroup analyses by the primary series strata will also be conducted for the primary endpoints, and all binding antibody, ACE2 binding inhibition, safety and breakthrough infection secondary endpoints. Tests of interaction will be done for the primary immunogenicity endpoint and secondary endpoint (i) (see 5.2 Secondary) by fitting a model with an interaction parameter between study arm and primary series strata.

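### The imputation model has no arm-by-primary-series term, although the SAP analyses and tests dose effects by primary series, so imputed series-specific effects shrink toward the common effect

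*SAP*

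**What the plan says.** SAP 6.15.1 sets out the hypothetical strategy: "Multiple imputation will be done using a univariate regression imputation model", with 50 imputations. It then gives a list introduced by "Covariates in the imputation model will be". The list holds trial vaccine, study arm, "primary series vaccine", age group, the two dose intervals, day of blood draw and the baseline level. For Month-6 and Month-12 endpoints it adds the outcome at earlier draws, provided the intercurrent event came after those visits. No interaction is named, and nothing says that imputation is run within arm or within series.

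SAP 6.15.2 applies the list to the chained-equations imputation of missing data: "Covariates in the imputation model will be the same as those specified for imputation under the hypothetical strategy". The same paragraph also appears under Tables 6 and 7, where it looks like a misplaced cross-reference. The operative text is 6.15.1 and 6.15.2. Titres are imputed, and seroresponse is derived from them.

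The analyses that may use these data are wider. The notes under Tables 6 and 7 say analyses are run "amongst all strata combined, and then stratified by the primary series strata". SAP 6.16 plans series subgroups for the primary endpoints and for the binding-antibody and ACE2-inhibition endpoints, among others. It tests interaction for the primary immunogenicity endpoint and secondary endpoint (i) "by fitting a model with an interaction parameter between study arm and primary series strata".

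The main analysis is complete case (Tables 10 and 14). Imputation enters in the sensitivity analysis when more than 5% are excluded, and in the hypothetical-strategy supplementary analyses.

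**The concern.** An imputation model should allow at least the effects that the later analysis will estimate. Here, read as written, it assumes one fractional-to-standard ratio for Sinopharm-, AstraZeneca- and Sputnik-primed participants. The subgroup analyses and the interaction test ask whether that ratio is the same. Imputed values drawn under the assumption pull the answer toward homogeneity.

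A series in which the half dose does worse would look somewhat better in the imputed analyses than it is, and the other series somewhat worse. These analyses exist to probe robustness, so they should not build in the homogeneity that the plan sets out to examine. Under the hypothetical strategy the imputed estimate is also the only one planned for that estimand.

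**Working it through.** **The plan's own figure.** The only related figure is the power for each series comparison in Protocol 11.1. With 95% response in both arms, a margin of -10 points and a two-sided 95% interval, power = Φ(0.10/√(2×0.95×0.05/n) − 1.96).
- n = 100: Φ(3.244 − 1.96) = 90.05%. The protocol says 90%.
- n = 200: Φ(4.588 − 1.96) = 99.57%. The protocol says above 99%.

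Both reproduce, and neither is in dispute.

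**Inputs.** Series sizes per arm are 200/100/100 (SAP 3.3), so the weights w are 0.50/0.25/0.25. The documents give no dose effects by series, no standard deviations and no missing fractions, so those below are assumptions. Missingness is taken as random within series.

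**Closed form on the log-titre scale.** Let d be the true effect in a series and m the share imputed there. With main effects only:
- common effect seen in the observed data: D = Σ w(1−m)d / Σ w(1−m)
- effect in a series after imputation: (1−m)d + mD

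Assume a GMR of 0.70 in Sinopharm (log −0.3567) and 1.00 in the other two. The true pooled log effect is 0.5 × −0.3567 = −0.1783, a GMR of 0.837.

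| Missing (Sinopharm/others) | D | Sinopharm after imputation | GMR | Pooled GMR |
|---|---|---|---|---|
| 10%/10% | −0.1783 | 0.9(−0.3567) + 0.1(−0.1783) = −0.3388 | 0.713 | 0.837 |
| 30%/30% | −0.1783 | 0.7(−0.3567) + 0.3(−0.1783) = −0.3032 | 0.739 | 0.837 |
| 50%/20% | 0.25(−0.3567)/0.65 = −0.1372 | 0.5(−0.3567) + 0.5(−0.1372) = −0.2469 | 0.781 | 0.872 |

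Simulations with proper imputation (residual SD 0.8) agree: Sinopharm about 0.71 to 0.72, 0.73 to 0.74 and 0.78. Adding the arm-by-series term returns about 0.70 for Sinopharm and 0.83 to 0.84 pooled.

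**Effect of an earlier titre.** Adding an earlier titre, as 6.15.1 allows at Months 6 and 12, with an assumed correlation of 0.6, brings Sinopharm to about 0.70, 0.71 and 0.73 to 0.74 in the three rows. With correlation 0.7 and the 50%/20% pattern it is 0.726.

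**Seroresponse.** A simulation of 300 trials derived seroresponse by SAP Table 5, with an assumed log effect of −0.5 in Sinopharm and none elsewhere. Differences are in percentage points.

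| Missing (Sinopharm/others) | Sinopharm: full data / main effects / with interaction | Common effect: full data / complete case / main effects / with interaction |
|---|---|---|
| 10%/10% | −20.7 / −19.8 / −20.8 | −10.3 / −10.4 / −10.2 / −10.3 |
| 20%/20% | −21.1 / −18.9 / −21.0 | −10.5 / −10.5 / −10.2 / −10.4 |
| 20%/5% | −20.8 / −18.2 / −20.5 | −10.5 / −9.5 / −9.4 / −10.4 |

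With the same dose effect in every series (log −0.2), the main-effects model shows no material bias.

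**Interval width.** In the 50%/20% case without an earlier titre, the mean standard error from Rubin's rules was 0.106, against an empirical standard deviation of about 0.083. Coverage for Sinopharm was about 84% to 88% across simulation runs. The standard errors are too large rather than too small, so the loss of coverage comes from bias.

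**The case against.** The strongest reply is that little depends on this. The imputed analyses are secondary. Table 14 repeats the main analysis, whose model has no interaction, so the pooled imputation is compatible with it. Table 14 does not itself call for series-stratified imputed results; that rests on the general notes under Tables 6 and 7. The interaction tests cover two Day-28 endpoints, and SAP 6.11 expects infections before that visit to be rare. All of this stands, and it is why the point is minor.

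The list is also generic to three studies. Trial vaccine is on it although Mongolia has only one, and the Table 14 note says "The specified supplementary analyses will be conducted for each endpoint, separately for each trial vaccine". The presence of vaccine and series on the list therefore does not prove that imputation is run across those groups. If the data were subset by series first, there would be no flattening. The SAP does not say so, and that silence is what needs settling.

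Three stronger readings are tempting, and none is supported:
- A reader might infer that the intervals are too narrow because they borrow a dose effect from other series. The standard errors above show the opposite.
- A reader might infer that the imputation creates a pooled bias. On the log scale there is none when missingness is equal across series. With 50%/20% missing, the complete-case common effect is shifted just as much (0.872 to 0.873, against 0.872 imputed). The imputation fails to remove the shift rather than causing it.
- A reader might infer that the primary non-inferiority conclusion is at risk. It comes from the complete-case analysis, which uses no imputed value.

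**Conclusion.** The point holds as a minor gap in specification. The covariate list omits a term that the planned subgroup and interaction analyses need. If dose effects differ by series, imputed series-specific effects shrink toward the common one in rough proportion to the share imputed. The shift is small at 10% missing, which is the more relevant range for Day 28. It is larger when missingness is heavy or unequal, and partly offset at Months 6 and 12 by the earlier titre, where the intercurrent event came after that visit.

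When missingness differs by series, a model with the interaction removes a pooled shift that both the main-effects imputation and the complete-case common effect retain. Every size quoted rests on assumed heterogeneity and missing fractions; with homogeneous dose effects there is no material bias. The reach is limited to the sensitivity analysis for more than 5% missing and the hypothetical-strategy supplementary analyses.

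**What to change.** In SAP 6.15.1 and 6.15.2, state that imputation is done separately by study arm, and within trial vaccine where a study has more than one, with primary series kept in the model. In Stata this is the by() option of mi impute. Adding arm-by-series terms (and arm-by-vaccine terms where relevant) would serve equally well. Imputing within full arm-by-series cells is optional. In Mongolia trial vaccine is constant, so only arm by series matters there. Remove or align the stray copies under Tables 6 and 7.

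The cost is one sentence in the SAP and one option in the code, with no new data. The downside is slightly more variable series-specific imputed estimates.
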